Stage related to study timeline	A major subdivision of the study timeline; begins and ends with major study milestones such as enrollment, randomization, completion of treatment, etc.
Stop study participation	Point/time at which the patient came in for a final evaluation visit or when study treatment was discontinued whichever is later
Study treatment	Includes any drug or combination of drugs in any study arm administered to the patient (subject) as part of the required study procedures, including placebo and active drug run-ins. In specific examples, it is important to judge investigational treatment component relationship relative to a study treatment combination; study treatment in this case refers to the investigational and non-investigational treatments in combination.
Study treatment discontinuation	Point/time when patient permanently stops taking study treatment for any reason
Variable	Identifier used in the data analysis; derived directly or indirectly from data collected using specified assessments at specified timepoints
Withdrawal of consent	Withdrawal of consent occurs only when a patient does not want to participate in the study any longer, and does not want any further visits or assessments, and does not want any further study related contact

Protocol summary:

Title	A multicenter phase II, open label, single arm study to evaluate the efficacy and safety of ruxolitinib in the treatment of anemic myelofibrosis patients.
Brief title	Anemia trial in MF patients
Sponsor and Clinical Phase	Novartis Phase II
Investigation type	Drug
Study type	Interventional
Purpose and rationale	This is a study of treatment with ruxolitinib in patients who present with transfusion dependent or independent anemia at screening defined as an hemoglobin <10 g/dL with 10 mg BID starting dose with subsequent up titrations depending on safety and efficacy. This dosing approach for anemic MF patients will be systematically studied in this prospective multicenter phase II open label single arm trial to determine if the levels of spleen length reduction and symptom improvement are consistent with those reported in previous clinical trials with ruxolitinib in patients with anemia and doses according to platelet counts at the moment of treatment initiation, and whether this lower starting dose and up titration approach may minimize the initial hemoglobin and platelet declines and transfusion requirements.

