6.4.3 Prohibited concomitant therapy

The following medications are prohibited during the study until treatment discontinuation:

- Concomitant use of another JAK inhibitor.
- Any investigational medication (other than ruxolitinib) that is not approved for any indication. Use of such medications within 30 days or 5 half-lives, whichever is longer, prior to the first dose of study drug and until treatment discontinuation is prohibited.
- Use of hydroxyurea, interferon, thalidomide, busulfan, lenalidomide, or anagrelide is not permitted at any time during participation in the study. These medications should be discontinued prior to Day 1 of ruxolitinib therapy. All adverse events attributed to these medications should be resolved prior to Day 1 of ruxolitinib treatment.
- Potent inducers of CYP3A4 ([Appendix 5](#)) are not permitted.
- Aspirin in doses exceeding 150 mg per day is prohibited.

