2.2.3 Per-Protocol set

The Per-Protocol Set (PPS) consists of a subset of the patients in the FAS who had no major protocol deviation.

The following major protocol deviations will lead to exclusion from the PPS:

- Patient with less than 12 years of age at screening
- Patients with unconfirmed diagnosis of PMF, PPV-MF or PET-MF, as reviewed by clinical team
- Patient without palpable splenomegaly or with a spleen length below 5 cm at baseline
- Patient with hemoglobin \geq than 10 g/dL at baseline
- Patient had prior treatment with any JAK1 or JAK2 inhibitor
- Patient has known hypersensitivity to ruxolitinib or other JAK1/JAK2 inhibitors, or to their excipients
- Treatment with another investigational medication or treated with an investigational medication within 30 days or 5 half-lives (whichever is longer) prior to the first dose of study drug
- Patient unable to comprehend or are unwilling to sign an ICF or Patient did not sign ICF or amended ICF
- Concomitant use of another JAK inhibitor
- Use of investigational medication not approved for any indication within 30 days or 5 half-lives, whichever is longer, prior to the first dose of study drug and until treatment discontinuation
- Use of hydroxyurea, interferon, thalidomide, busulfan, lenalidomide, or anagrelide on Day 1 of ruxolitinib therapy and at any time during participation in the study
- Use of potent CYP3A4 inducers in combination with ruxolitinib

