2.5.4 Supportive and Sensitivity analyses

The primary analysis (as described in Section 2.5.2) will also be repeated on the PPS. Furthermore, the primary endpoint will be analyzed on patients with non-missing spleen length at both baseline and Week 24. Proportion of patients achieving a 50% reduction in spleen length

at any time during the study will also be reported along with corresponding exact 95% confidence interval using Clopper and Pearson exact method.

IWG-MRT response criteria will also be used to analyze spleen length response rate at Week 24. Response as per IWG-MRT criteria is defined as follows:

- A baseline splenomegaly that is palpable at 5-10 cm, below the LCM at baseline, becomes not palpable, post-baseline or
- A baseline splenomegaly that is palpable at >10 cm at baseline, below the LCM, decreases by $\geq 50\%$, post-baseline
- A baseline splenomegaly that is palpable at <5 cm at baseline, below the LCM, is not eligible for spleen response

Patients meeting response criteria as per above definition will be considered as responders or else will be non-responders. The point estimate of the proportion of responders along with corresponding exact 95% confidence interval using Clopper and Pearson exact method will be presented at Week 24. The same analysis will be repeated for proportion of responders as per IWG-MRT response criteria for spleen at any time during the study.

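### The per-protocol exclusion for hydroxyurea and five other drugs stops neither at Week 24 nor at the last ruxolitinib dose, so later events can change the supportive Week 24 result

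*SAP*

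**What the plan says.** SAP 2.2.3 lists the major deviations that take a patient out of the PPS. One of them is "Use of hydroxyurea, interferon, thalidomide, busulfan, lenalidomide, or anagrelide on Day 1 of ruxolitinib therapy and at any time during participation in the study". The PPS has a single use: protocol 10.1.3 makes it supportive for the primary endpoint, and SAP 2.5.4 states "The primary analysis (as described in Section 2.5.2) will also be repeated on the PPS".

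The other drug-use exclusions in the same list are narrower. The one for unapproved investigational drugs covers use "prior to the first dose of study drug and until treatment discontinuation". The remaining two read "Concomitant use of another JAK inhibitor" and "Use of potent CYP3A4 inducers in combination with ruxolitinib". None of them stops at Week 24.

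Three protocol texts bear on the open-ended item:

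- **Protocol 6.4.3** has the same six drugs under a lead-in that reads "The following medications are prohibited during the study until treatment discontinuation", although the individual bullet there uses the same open period as the SAP.
- **Protocol 6.4.1** requires a patient who needs another anticancer agent to be withdrawn from the study first.
- **The protocol glossary** defines the end of study participation as "Point/time at which the patient came in for a final evaluation visit or when study treatment was discontinued whichever is later".

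Participation can therefore continue after the last dose, since protocol 4.1 and 7.1.6 require 30 days of safety evaluation, including a review of concomitant medication. Treatment itself runs until 48 weeks after the last patient starts.

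**The concern.** A per-protocol repeat of a Week 24 endpoint should drop only patients whose deviation could have affected the Week 24 measurement. This exclusion can reach two other groups.

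1. **Use after the Week 24 palpation.** The drug cannot have influenced the measurement, yet the patient leaves. Responders and non-responders can both be lost, so the PPS rate may move either way. SAP 2.1 uses all data up to the cut-off, so if the PPS is derived again for the final report, its Week 24 result could change through later events alone.
2. **Use after stopping ruxolitinib before Week 24, while still in follow-up.** SAP 2.5.3 counts patients who withdraw early, or have no Week 24 spleen length, as non-responders. Removing them deletes counted failures from the denominator, which can only raise the rate.

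At stake is the value of the PPS result as a check on the FAS result. The two could disagree because of who was removed and not because of how the drug performed under the protocol.

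**Working it through.** **Inputs from the documents**

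- Planned size 50 (SAP 3).
- Success rule (SAP 2.5.2): (a) observed rate at least 25%, and (b) posterior probability that the true rate is 15% or lower is below 10%.
- Prior Beta(1/3, 1), so with y responders among n patients the posterior is Beta(1/3 + y, 1 + n − y) (SAP 5.6.1).

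**Assumptions**

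- k, the number of non-responders this exclusion removes, is not in the documents. It is varied from 0 to 12.
- The repeat on the PPS uses the number of patients in the PPS as n.

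**Step 1: reproduce the plan.** The posterior probability at 0.15 for 11 to 16 responders of 50 is 0.1014, 0.0520, 0.0243, 0.0104, 0.0041 and 0.0015. With at least 13 of 50 required, P(Y ≥ 13) for Y ~ Bin(50, p) is 0.0301 at p = 15% and 0.9339 at p = 35%. All agree with SAP 3.

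**Step 2: remove non-responders from a failing result.**

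- 12/50 = 24.0% fails (a). Without two non-responders it is 12/48 = 25.0%. The posterior Beta(12.333, 37) puts 0.0390 at or below 15%, so both criteria are met.
- 11/50 = 22.0% needs six removals: 11/44 = 25.0%, posterior 0.0462.
- 10/50 = 20.0% needs ten removals: 10/40 = 25.0%, posterior 0.0547.

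**Step 3: chance that the PPS repeat passes.** For each k, take r as the smallest y that meets (a) and (b) at n = 50 − k, then compute P(Y ≥ r) with Y ~ Bin(50, p). Here every removed patient is a non-responder.

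| k | n | r | Posterior at r | Pass, true rate 15% | Pass, true rate 20% |
|---|---|---|---|---|---|
| 0 | 50 | 13 | 0.0243 | 0.0301 | 0.1861 |
| 1 | 49 | 13 | 0.0206 | 0.0301 | 0.1861 |
| 2–5 | 48–45 | 12 | 0.0390–0.0242 | 0.0628 | 0.2893 |
| 6–9 | 44–41 | 11 | 0.0462–0.0284 | 0.1199 | 0.4164 |
| 10–12 | 40–38 | 10 | 0.0547–0.0396 | 0.2089 | 0.5563 |

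If instead each non-responder independently has a 5%, 10%, 15% or 20% chance of removal (assumed), the pass probability at a true rate of 15% is 0.0495, 0.0710, 0.0994 or 0.1365.

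**Step 4: remove a responder from a passing result.** 13/50 = 26.0% passes. If one Week 24 responder later takes a listed drug and is dropped, the result is 12/49 = 24.5% with posterior 0.0452. Criterion (a) fails.

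**The case against.** Much of the case against a broader claim stands.

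- **Are all the PPS exclusions open-ended?** A reader might infer so, but they are not. Three of the four drug-use items end at treatment discontinuation or require use together with ruxolitinib. Only the hydroxyurea-list item lacks a last-dose limit. What all four lack is a cap at Week 24.
- **Are early stoppers who switch drug certain to be removed?** No. If the lead-in of protocol 6.4.3 governs, use after stopping is not a deviation. If protocol 6.4.1 is followed, the patient may have left the study before the new drug starts. The glossary does not say whether its final evaluation visit is the end-of-treatment visit or the 30-day visit. The texts are not aligned, and the literal reading of SAP 2.2.3 is one of several.
- **Is the PPS result necessarily inflated?** No. Upward movement is assured only for patients who stopped before Week 24. Later use can remove responders, as Step 4 shows.
- **Are the larger pass probabilities forecasts?** No. They assume that every removed patient is a non-responder, and nothing in the documents supports a particular k.
- **Could a PPS pass rescue an FAS failure?** Nothing in the plan allows that. The success decision rests on the FAS (protocol 10.4.2, SAP 2.5.1), and SAP 2.5.4 also plans an analysis of patients with both spleen measurements.

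A reader might also see selection on outcome in the item "Patients with unconfirmed diagnosis of PMF, PPV-MF or PET-MF, as reviewed by clinical team" or in the consent item. The first does not require review without sight of response, but diagnosis is a screening item and protocol 7.1.2.1 has the sponsor confirm eligibility before treatment is assigned. The documents show no link between the consent item and response. Both are minor.

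None of this supplies the missing time limit in SAP 2.2.3.

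**Conclusion.** The point holds for one exclusion and one supportive analysis. As written, SAP 2.2.3 lets use of six named drugs after the Week 24 assessment, and on a literal reading after the last ruxolitinib dose, decide who enters the per-protocol repeat of the Week 24 rule. Post-Week-24 use can shift that result in either direction; removal of early stoppers can only shift it upward.

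Two non-responders removed, or one responder removed, is enough to reverse a result next to the threshold. At a true rate of 15%, removing two to five non-responders doubles the pass probability from 0.0301 to 0.0628. Removing six to nine takes it to 0.1199, above the 10% false-success limit stated in SAP 3 for the design. These figures rest on an assumed k made up entirely of non-responders. How many patients would be affected cannot be known from the documents. The FAS decision does not change.

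**What to change.** In SAP 2.2.3, state that for the Week 24 analysis a post-baseline drug-use deviation excludes a patient from the PPS only if it occurs on or before the earlier of the Week 24 spleen assessment and the last ruxolitinib dose. All other patients stay in with their FAS response status. Apply this to all the drug-use items, since none is capped at Week 24.

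Separately, the sponsor should reconcile protocol 6.4.1, both parts of protocol 6.4.3 and SAP 2.2.3 on when use of these drugs counts as a deviation. That is a clinical rule for the sponsor to settle, and the PPS date limit does not depend on the answer.

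The cost is one sentence in the SAP and one date check in the PPS program. SAP 2.4.2 already separates therapies that start after the last non-zero dose, and no new data are needed.

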2.2.4 Subgroup of interest

Not Applicable.

2.3 Patient disposition, demographics and other baseline characteristics

Demographic and other baseline data (including disease characteristics) will be listed and summarized descriptively for the FAS.

Categorical data will be presented as frequencies and percentages. For continuous data, mean, standard deviation, median, 25th and 75th percentiles, minimum, and maximum will be presented.

Relevant medical histories and current medical at baseline will be summarized separately for ongoing and historical medical conditions by system organ class and preferred term, for the FAS.

2.3.1 Patient disposition

Enrollment by country and center will be summarized for all screened patients and also by treatment arm using the FAS. The number (%) of treated patients included in the FAS will be presented.

The following summaries will be provided (with % based on the total number of FAS patients):

- Number (%) of patients enrolled,
- Number (%) of patients who completed the study treatment,
- Number (%) of patients who are still on-treatment
- Number (%) of patients who discontinued the study treatment and reasons for discontinuation,
- Number (%) of patients who discontinued the study and reasons for discontinuation.

Disposition data will also be listed.

Protocol deviations

The number (%) of patients in the FAS with any protocol deviation will be tabulated by deviation category (as specified in the study Data Handling Plan) by overall for the FAS. All protocol deviations will be listed.

Analysis sets

The number (%) of patients in each analysis set (defined in Section 2.2) will be summarized by overall.

2.4 Treatments (study treatment, rescue medication, concomitant therapies, compliance)

2.4.1 Study treatment / compliance

Duration of exposure, actual cumulative dose, dose intensity (DI) and relative dose intensity (RDI) will be summarized for Safety Set.

Duration of exposure will be categorized into time intervals; frequency counts and percentages will be presented for the number (%) of patients in each interval. The number (%) of patients who have dose changes or interruption, and the reasons, will be summarized for the Safety Set.

Subject level listings of all doses administered while on treatment along with the reasons for a dose change will be produced.

Duration of exposure to study treatment:

Duration of exposure to study treatment is considered by taking into account the duration of exposure to the investigational drug:

Duration of exposure (days) to study treatment = [(date of last non-zero dose administration of study treatment) – (date of first non-zero dose administration of study treatment) + 1 day].

(see Section 2.1.1.3 for definition for the dates first/last administration).

The duration includes the periods of temporary ruxolitinib interruption (s).

The duration of exposure will be summarized by descriptive statistics, as well as by duration category (<= 4 Weeks, >4 – <= 8 Weeks, >8 – <= 12 Weeks, >12 – <= 16 Weeks, >16 – <= 20 Weeks, >20 – <= 24 Weeks, >24 – <= 36 Weeks, and in interval of 12 Weeks thereafter).

Duration of on study:

The duration of on study is defined as the time interval from the enrollment date to the last contact date.

Duration of on study (days) = [(end of study date – (enrollment date) +1 day]

The duration of study will be summarized by descriptive statistics, as well as by duration category (<= 4 Weeks, >4 – <= 8 Weeks, >8 – <= 12 Weeks, >12 – <= 16 Weeks, >16 – <= 20 Weeks, >20 – <= 24 Weeks, >24 – <= 36 Weeks, and in interval of 12 Weeks thereafter).

Cumulative dose:

Cumulative dose of a study treatment is defined as the total dose given during the study treatment exposure and will be summarized for Safety Set.

The **planned cumulative dose** for a study treatment component refers to the total planned dose as per the protocol up to the last date of investigational drug administration.

The **actual cumulative dose** refers to the total actual dose administered, over the duration for which the subject is on the study treatment as documented in the Dose Administration eCRF.

For patients who did not take any drug, the cumulative dose is by definition equal to zero.

The actual cumulative dose is the sum of the non-zero doses recorded over the dosing period and the planned cumulative dose is the planned starting dose summed over the same dosing period.

Dose intensity and relative dose intensity

Dose intensity (DI) for patients with non-zero duration of exposure is defined as follows:

DI (mg / day) = Actual Cumulative dose (mg) / Duration of exposure to study treatment (day).

For patients who did not take any drug the DI is by definition equal to zero.

Planned dose intensity (PDI) is defined as follows:

PDI (mg / day) = Planned Cumulative dose (mg) / Duration of exposure (day).

Relative dose intensity (RDI) is defined as follows:

RDI = DI (mg / day) / PDI (mg / day).

DI and RDI will be summarized for Safety Set.

Dose reductions, interruptions or permanent discontinuations:

The number of subjects who have dose reductions, permanent discontinuations or interruptions, and the reasons, will be summarized for Safety Set.

‘Dose interrupted’, and ‘Dose permanently discontinued’ fields from the Dosage Administration CRF pages (DAR) will be used to determine the dose reductions, dose interruptions, and permanent discontinuations, respectively.

The corresponding fields ‘Reason for dose change/dose interrupted’ and ‘Reason for permanent discontinuation’ will be used to summarize the reasons.

A dose change is either ‘change in prescribed dose level’ or ‘dosing error’ where actual dose administered/total daily dose is different from the prescribed dose.

For the purpose of summarizing interruptions and reasons, in case multiple entries for interruption that are entered on consecutive days with different reasons will be counted as separate interruptions. However, if the reason is the same in this mentioned multiple entries on consecutive days, then it will be counted as one interruption.

Reduction: A dose change where the prescribed dose level is lower than the previous prescribed dose level or where the actual dose administered/total daily dose is lower than the calculated dose amount based on the prescribed dose. Therefore any dose change to correct a dosing error will not be considered a dose reduction. Only dose change is collected in the CRF, number of reductions will be derived programmatically based on the change and the direction of the change.

2.4.2 Prior, concomitant and post therapies

Prior medications or therapies are defined as drugs or therapies taken and stopped prior to first dose of study treatment. Post-treatment therapies will include all therapies that start after the last non-zero dose of study treatment.

Concomitant medications prior to and after the start of ruxolitinib will be listed and summarized according to the Anatomical Therapeutic Chemical (ATC) classification system by means of frequency counts and percentages. These summaries will include medications starting on or after the start of study treatment or medications starting prior to the start of study treatment and continuing after the start of study treatment.

Any prior concomitant medications or significant non-drug therapies starting and ending prior to the start of study treatment will be listed.

2.5 Analysis of the primary objective

The primary objective of this study is to determine the spleen length response rate at week 24.

2.5.1 Primary endpoint

The primary efficacy variable for this study is the proportion of patients achieving a 50% reduction in spleen length at Week 24. The FAS will be used for the primary analysis.

2.5.2 Statistical hypothesis, model, and method of analysis

The assessment of primary efficacy of study treatment will be based on the calculation of the observed proportion of patients with spleen length response at Week 24 and its posterior distribution using a Beta-binomial model. A patient will be a responder if he/she achieves a 50% reduction in spleen length at Week 24.

Study treatment will be declared efficacious if the following criteria are met:

- a. Observed proportion of patients with $\geq 50\%$ reduction in spleen length at Week 24 $\geq 25\%$
- b. Probability of true response rate $\leq 15\%$ (considered not clinically meaningful) is less than 10%

With 50 patients, criteria 'a' and 'b' will be met if the observed responder rate is $\geq 25\%$, i.e., at least 13 patients out of 50 patients have a response at Week 24 which will give a probability of "not being clinically meaningful (response $\leq 15\%$)" of 0.0243.

The primary analysis will be performed when all the enrolled patients have been treated with ruxolitinib for 24 weeks or discontinued prior to Week 24. The point estimate of the proportion of patients achieving $\geq 50\%$ reduction in spleen length at Week 24 along with corresponding exact 95% confidence interval using Clopper and Pearson exact method will be presented.

